10.3 Vital Signs and Weight

Weight and vital signs (including systolic blood pressure, diastolic blood pressure, pulse rate, respiratory rate, and body temperature) will be summarized for each treatment group. Descriptive statistics of each parameter at baseline will be provided along with the change from parent-study baseline at each subsequent visit. A subject-level listing will also be provided.

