4.2 SCIENTIFIC RATIONALE FOR STUDY DESIGN

SM04690-OA-07 is a long-term study designed to evaluate the safety and efficacy of a second year and long-term use of LOR in subjects with OA of the knee. The placebo used in this study is the same vehicle used to formulate LOR but without the active ingredient. A vehicle-controlled single-blind design is considered appropriate for year one of this study as it allows for evaluation of the safety and efficacy of the LOR molecule alone through an unbiased comparison of the active and vehicle injections over a total of 2 years. Beyond 2 years (including parent-study SM04690-OA-11 participation), crossing subjects on placebo over to LOR will provide additional long-term safety information in a group of subjects not previously treated with LOR.

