10.4.2 ANALYSIS OF SAFETY ENDPOINT(S)

Safety analyses will be performed on subjects who receive a study injection. Safety assessments include physical examinations, vital signs, clinical laboratory tests, solicitation of AEs and concomitant medications, and general medical evaluations. No formal statistical analyses are planned. Safety will be evaluated based on the incidence, seriousness, severity, and relationship of AEs and by changes in clinical laboratory parameters and vital signs, relative to parent-study baseline. For subjects who cross over from placebo to LOR, subsequent changes in laboratory parameters and vital signs will be relative to Visit 3E.

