10.4.4 BASELINE DESCRIPTIVE STATISTICS

Baseline is defined as the last value recorded before a study injection of the parent study (i.e., parent-study baseline). Baseline descriptive statistics from parent study will include age, sex, race, height, weight, body mass index (BMI), mJSW, Kellgren-Lawrence (KL) grade, and the presence of symptomatic and radiographic OA.

For subjects who cross over from placebo to LOR, Visit 3E (i.e., first exposure to LOR) will serve as an additional reference point for analysis.

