3.2.3 Safety Endpoints

1. Adverse events (AEs) and serious adverse events (SAEs) (incidence, severity, and relationship to study drug) over the course of the study up to the end of the single-blind and placebo-controlled portion of the trial (i.e., prior to Second OA-07 injection [Lorecivivint only])
2. Clinically significant changes from parent-study-baseline clinical laboratory measures and vital signs, as assessed by the Investigator, over the course of the study up to Visit 3E (Week 48)

3. Change in serum bone biomarkers (N-terminal propeptides of procollagen type I [P1NP] and β -C-terminal telopeptide [β -CTX]) from parent-study baseline, and change in a serum cartilage biomarker (cartilage oligomeric matrix protein [COMP]) from parent-study baseline at Visit 3E (Week 48)

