10.2 Clinical Laboratory Evaluations

All chemistry, hematology and urinalysis results from the central laboratory will be summarized into shift tables as normal, non-clinically significant abnormal, and clinically significant abnormal. Assessments of clinical significance for abnormal values were made by the investigator on results that were outside of the normal range. Shift tables will compare the number and percent of assessments from each visit to baseline values for each treatment group.

All chemistry and hematology results from the central laboratory will be summarized for each treatment group. Descriptive statistics of each laboratory test at all timepoints will be provided along with the change from baseline at each subsequent visit. If a result is below the limit of quantification, it will be set to half the value for analysis (e.g., “< 3” will be analyzed as 1.5). The International System of Units (SI) will be used for all summaries.

Abnormal chemistry, hematology, urinalysis, and urine microscopy results for each subject will be provided in listings that will include laboratory test name, result, normal range, and an explanation for clinically significant values.

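### SAP 10.3 drops the protocol's Visit 3E reference for vital signs after crossover, SAP 10.2 leaves the laboratory reference open, and Section 13 declares neither

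*SAP*

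**What the plan says.** **Protocol.** Section 10.4.2, repeated in the synopsis, uses parent-study baseline for laboratory and vital-sign changes in general and then makes an exception: "For subjects who cross over from placebo to LOR, subsequent changes in laboratory parameters and vital signs will be relative to Visit 3E". Section 10.4.4 says of the same subjects that "Visit 3E (i.e., first exposure to LOR) will serve as an additional reference point for analysis". Section 3.2.1 runs the laboratory and vital-sign endpoint over the whole study. Section 4.2 gives the reason for the crossover: "crossing subjects on placebo over to LOR will provide additional long-term safety information in a group of subjects not previously treated with LOR".

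**SAP.**
- Section 10.3 covers weight and vital signs: "Descriptive statistics of each parameter at baseline will be provided along with the change from parent-study baseline at each subsequent visit". The summary is by treatment group and has no exception for crossover subjects.
- Section 10.2 covers laboratory data: "Descriptive statistics of each laboratory test at all timepoints will be provided along with the change from baseline at each subsequent visit". On shifts it says: "Shift tables will compare the number and percent of assessments from each visit to baseline values for each treatment group". It does not say which baseline is meant.
- Section 7.1.1 defines three baselines for any parameter: parent-study, OA-07-study and Visit 3E. The Visit 3E baseline is used only in the concordance analysis (9.6.4), which is an efficacy analysis.
- Section 3.2.3, item 2, names parent-study baseline for laboratory measures and vital signs but ends the endpoint at Visit 3E.
- Section 13 lists changes to efficacy endpoint categories, analysis sets, the MMRM, the NSAID/acetaminophen sensitivity analysis, open-label efficacy testing and the OMERACT-OARSI responders. It lists no change to the safety analysis.

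**The concern.** Placebo subjects first receive LOR at Visit 3E, and injection is the last procedure at that visit (Protocol 7.3.4, footnote b). The Visit 3E laboratory and vital-sign values are therefore clean pre-exposure values. The protocol uses them as the reference for what follows.

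If change at later visits is taken from parent-study baseline, it also contains whatever happened during roughly two years on placebo. Shift tables built on that baseline would have the same problem. An abnormality that arose on placebo would appear as a shift. One that was present at parent-study baseline, had resolved by Visit 3E and recurred after LOR would appear as no shift.

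What is at stake is the readability of the laboratory and vital-sign summaries in the group whose added safety information Protocol 4.2 gives as the reason for the crossover.

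**Working it through.** The plan states no figure on this point, so there is none to reproduce. The check compares the texts and then works out what interval the SAP rule covers.

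**1. Texts side by side, subjects crossing from placebo, visits after Visit 3E**

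| Item | Protocol | SAP | Result |
|---|---|---|---|
| Vital signs, reference | Visit 3E (10.4.2) | Parent-study baseline (10.3) | Contradiction |
| Laboratory, reference | Visit 3E (10.4.2) | Unspecified baseline (10.2) | Rule omitted, ambiguous |
| Grouping after crossover | Not specified | Treatment group, undefined (10.2, 10.3) | Ambiguous |
| Endpoint period | Whole study (3.2.1) | To Visit 3E (3.2.3, item 2) | Shortened |
| Declared in Section 13 | – | No | Undeclared |

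**2. Inputs for the timeline**
- Parent-study end of study: Week 56 (Protocol 7.3.1).
- Gap from there to Visit 1E: 0 to 6 weeks (Protocol 7.3.1).
- Visit 3E: Week 48 ± 4 weeks (Protocol 7.3.2).
- First scheduled laboratory and vital-sign visit after crossover: Visit 6E, Week 100 ± 4 weeks (Protocol 7.1.1, 7.2.1, 7.3.2). SAP 4.1 says active subjects were asked to continue to this visit.
- Assumption: parent-study Week 56 is counted from the parent-study baseline.

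**3. Interval covered at Visit 6E**
- From parent-study baseline: 56 + (0 to 6) + 100 = 156 to 162 weeks.
- Part before any LOR: 56 + (0 to 6) + 48 = 104 to 110 weeks.
- Share before any LOR: 104/156 = 66.7%; 110/162 = 67.9%.
- Extremes of the visit windows: (56 + 0 + 44)/(56 + 0 + 104) = 100/160 = 62.5%; (56 + 6 + 52)/(56 + 6 + 96) = 114/158 = 72.2%.
- From Visit 3E: 100 − 48 = 52 weeks, all after first exposure.

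**4. What the SAP quantity contains**

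For each subject, (Visit 6E − parent baseline) = (Visit 3E − parent baseline) + (Visit 6E − Visit 3E), that is, placebo-period change plus post-LOR change.

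The following values are assumed, in SD units. Take a true post-LOR shift of +0.2:
- drift −0.2: reported change −0.2 + 0.2 = 0.0;
- drift 0: reported change 0 + 0.2 = +0.2;
- drift +0.2: reported change 0.2 + 0.2 = +0.4.

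From Visit 3E, the answer is +0.2 each time. The parent-baseline change can therefore hide the shift, leave it as it is or enlarge it.

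**5. Spread (illustrative, equal variances at all visits)**

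The SD of the parent-baseline change divided by the SD of the Visit 3E change is √[(1 − r13)/(1 − r23)]. Here r13 is the correlation of parent baseline with Visit 6E, and r23 that of Visit 3E with Visit 6E. For assumed r13 of 0.4 to 0.7 and r23 of 0.5 to 0.8, with r23 at least r13, the ratio runs from 1.0 (equal correlations) to √(0.6/0.2) = 1.73. The documents give no correlations.

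**The case against.** A good deal can be said for the SAP, and several stronger readings do not survive.

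- **Laboratory data.** A reader might infer that the SAP also contradicts the protocol here. It does not say so. Section 10.2 names no baseline, and the parent-study wording in 3.2.3 belongs to an endpoint that ends at Visit 3E. This is an omission and an ambiguity.
- **Labelling.** A reader might infer that Visit 6E values taken after LOR will be shown in a placebo column. No text says so. The Safety Analysis Set is analysed as treated in the current study (SAP 6.3), and a Placebo-LOR group exists in SAP 9.6.5.1, though only for efficacy. The defect is an undefined label.
- **Dilution.** A reader might infer that a LOR signal is weakened. Drift could equally inflate it, and the 67% is a share of elapsed time, not a measure of bias.
- **Unique comparison.** A reader might take the crossover group as the only within-subject comparison off and on LOR. LOR-arm subjects also have a pre-LOR value at parent-study baseline, and Protocol 4.2 promises only additional long-term safety information.
- **Existing safeguards.** Clinically significant laboratory and vital-sign abnormalities are to be reported as adverse events (Protocol 7.1.1, 7.2.1). SAP 10.1 tabulates these by OA-07 injection period, independently of any baseline. Section 10.2 gives laboratory statistics at all timepoints and listings of abnormal results; 10.3 gives a vital-sign listing. A mean post-LOR change could be approximated by subtracting the Visit 3E mean change from the Visit 6E mean change, but only in the same subjects, and without its SD or range.
- **Sensitivity.** The first scheduled reading after crossover comes about 52 weeks after the injection, so it is a weak detector of an early effect under either baseline.
- **Softer protocol wording.** Protocol 10.4.4 calls Visit 3E an additional reference point, so parent-baseline summaries are not wrong in themselves.

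All of this limits the consequences. It does not remove the conflict: 10.4.2 states the rule directly for laboratory parameters and vital signs. Even on the softer reading, SAP 10.3 plans no Visit 3E-referenced summary, and 10.2 specifies none.

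**Conclusion.** The point holds in a limited form. For vital signs, SAP 10.3 contradicts Protocol 10.4.2 in crossover subjects. For laboratory data, SAP 10.2 omits the protocol rule and leaves the reference open. Both sections leave the post-crossover groups undefined, SAP 3.2.3 shortens the endpoint, and none of this is declared.

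The size that can be stated is one of time. The Visit 6E vital-sign change covers about 156 to 162 weeks, of which about 67% (62.5% to 72.2% at the window extremes) precede any LOR, against about 52 weeks from Visit 3E. The same applies to laboratory change only if parent-study baseline is the one used. Placebo-period drift is then confounded with post-LOR change. The documents do not allow a statement of how far, or in which direction, the summaries would be distorted.

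No formal safety tests are planned (SAP Section 10), so no error rate is affected. The change should be made because the stated rule departs from the protocol and the remedy is already defined in the SAP.

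**What to change.** 1. In SAP 10.2 and 10.3, for visits after Visit 3E, present Placebo-LOR and LOR-LOR separately, with the groups as in 9.6.5.1.
2. For Placebo-LOR, use the Visit 3E baseline of 7.1.1 for vital-sign change, laboratory change and laboratory shift tables. Parent-study-baseline summaries may be kept as an addition.
3. Name the baseline used in 10.2 for every table.
4. Align 3.2.3, item 2, with Protocol 3.2.1, so that the endpoint continues after Visit 3E.
5. For any of these not adopted, declare and justify the departure in Section 13.
6. Add a table note that the Placebo-LOR change (about 52 weeks) and the LOR-LOR change from parent-study baseline (about 156 weeks) cover different intervals and are not directly comparable. Alternatively, also show the Visit 3E-referenced change for LOR-LOR.

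The cost is SAP wording, a baseline flag and a re-run of planned tables. No new data are needed.

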10.4 Physical Examination

Results of the general physical and knee examinations were noted in the source documents. Any clinically significant finding noted prior to study medication injection was recorded as medical history. If it was found after study medication injection, it was reported as an AE.

11. OTHER/EXPLORATORY ANALYSIS

11.1 Biomarkers

Parent-study baseline-adjusted ANCOVA will be used to assess change in biomarkers COMP, P1NP and β -CT and evaluated at Visit 3E (Week 48). Unadjusted 95% confidence intervals and P values will be reported.

A statistical description of each biomarker at baseline will be provided along with the change from parent-study baseline at Visit 3E (Week 48). A subject-level listing will also be provided. COMP values will be summarized and listed in ng/mL (i.e. original results in pg/mL will be divided by 1000).

12. MEDICATIONS

The summary of medications will be performed on the SAS.

12.1 Concomitant Medication

The World Health Organization Drug Dictionary (WHODD) will be used to classify concomitant medications by Anatomical Main Group (Anatomical Therapeutic Chemical, ATC, Level 1), Therapeutic Subgroup (ATC Level 2), and preferred term. Concomitant medication (CM) usage will be summarized by the number and percentage of subjects receiving each medication by treatment group. A similar table will be used to summarize the subset of CMs identified as NSAID/Acetaminophen medications.

Additional tables will summarize CMs that started prior to a Second OA-07 Injection (single-blind, placebo-controlled period of the study; including all CMs for subjects who only received

the First OA-07 Injection). If a medication start or end date is incomplete, it will be imputed in a way that assumes maximum exposure time (see table in [Appendix 3 – Partial Date Imputation](#)). Subject-level listings containing concomitant medications (WHODD coding), and procedures/non-drug therapies (MedDRA coding) will be provided and will display the dates as they were entered (not the imputed version described above).

12.2 Exposure and Compliance

A subject-level exposure listing will be provided.

13. CHANGES TO PLANNED ANALYSIS

Change	Protocol Section	Rationale
Per protocol, efficacy endpoints were simply listed. In the SAP, we clearly define efficacy endpoints into categories of primary, secondary, and other. Additionally, an mFAS for completers of Visit 3E (Week 48) was defined as well as a CAS for subjects with an available mJSW at Visit 6E (Week 100).	3.2 and 6.4	Based on study team decision and clinicaltrials.gov reporting.
Per protocol, mixed-effects models for repeated measures (MMRM) would be used. In SAP we describe the use of ANCOVA. Additionally, the protocol mentioned ‘potential confounding effect of change in NSAID/acetaminophen usage on the treatment effect’ will not be considered as a sensitivity analysis.	9	More appropriate model and elimination of a sensitivity analysis given the spacing of the visits/assessment collection in the OA-07 study as compared to the OA-11 study.
Per protocol, “After all subjects have received LOR at Visit 3E, all further efficacy analyses will be descriptive in nature.” See section 9.4.4 regarding the efficacy analysis pertaining to the “Open-label” portion of the study.	9	Based on study team decision.
Per protocol, “Outcome Measures in Rheumatology Clinical Trials (OMERACT)-Osteoarthritis Research Society International (OARSI) responders and ‘strict’ responders” would be estimated. Only “strict” responders will be estimated.	10.4.3	One of the components comprising OMERACT-OARSI response, Patient Global Assessment of Disease Activity, was not collected.

15.2 Appendix 2 – Estimands

	Estimator	Variable	Population	Intercurrent events	Population level summary
Primary	Main	Change from parent-study baseline in mJSW at Visit 3E (Week 48)	FAS	Prohibited medications and NSAID/acetaminophen use: treatment policy strategy; analysis will be conducted regardless of use of prohibited medications or NSAID/acetaminophen use.	Difference in the change from parent-study baseline between LOR and placebo using parent-study baseline-adjusted ANCOVA with available data.
	Sensitivity 1	Change from parent-study baseline in mJSW at Visit 3E (Week 48)	FAS	Prohibited medications and NSAID/acetaminophen use: treatment policy strategy; analysis will be conducted regardless of use of prohibited medications or NSAID/acetaminophen use.	Difference in the change from parent-study baseline between LOR and placebo using parent-study baseline-adjusted ANCOVA with missing data imputed using the MI method.
	Sensitivity 2	Change from parent-study baseline in mJSW at Visit 3E (Week 48)	mFAS	Prohibited medications and NSAID/acetaminophen use: treatment policy strategy; analysis will be conducted regardless of use of prohibited medications or NSAID/acetaminophen use.	Difference in the change from parent-study baseline between LOR and placebo using parent-study baseline-adjusted ANCOVA with available data.
	Sensitivity 3	Change from parent-study baseline in mJSW at Visit 3E (Week 48)	PPAS	1) Prohibited medications: principal stratum strategy; subjects who used prohibited medications will be excluded from this analysis. 2) NSAID/acetaminophen: treatment policy strategy; analysis will be conducted regardless of NSAID/acetaminophen use.	Difference in the change from parent-study baseline between LOR and placebo using parent-study baseline-adjusted ANCOVA.
Estimand is repeated using the OA-07-study baseline as Secondary					

Secondary	Estimator	Variable	Population	Other intercurrent events	Population level summary
	Main	Change from parent-study baseline in Pain NRS at Visit 3E (Week 48)	FAS	Prohibited medications and NSAID/acetaminophen use: treatment policy strategy; analysis will be conducted regardless of use of prohibited medications or NSAID/acetaminophen use.	Difference in the change from parent-study baseline between LOR and placebo using parent-study baseline-adjusted ANCOVA with available data.
	Sensitivity 1	Change from parent-study baseline in Pain NRS at Visit 3E (Week 48)	FAS	Prohibited medications and NSAID/acetaminophen use: treatment policy strategy; analysis will be conducted regardless of use of prohibited medications or NSAID/acetaminophen use.	Difference in the change from parent-study baseline between LOR and placebo using parent-study baseline-adjusted ANCOVA with missing data imputed using the MI method.
	Sensitivity 2	Change from parent-study baseline in Pain NRS at Visit 3E (Week 48)	mFAS	Prohibited medications and NSAID/acetaminophen use: treatment policy strategy; analysis will be conducted regardless of use of prohibited medications or NSAID/acetaminophen use.	Difference in the change from parent-study baseline between LOR and placebo using parent-study baseline-adjusted ANCOVA with available data.
	Sensitivity 3	Change from parent-study baseline in Pain NRS at Visit 3E (Week 48)	PPAS	1) Prohibited medications: principal stratum strategy; subjects who used prohibited medications will be excluded from this analysis. 2) NSAID/acetaminophen: treatment policy strategy; analysis will be conducted regardless of NSAID/acetaminophen use.	Difference in the change from parent-study baseline between LOR and placebo using parent-study baseline-adjusted ANCOVA.
Estimand is repeated using the OA-07-study baseline					

Secondary	Estimator	Variable	Population	Other intercurrent events	Population level summary
	Main	Change from parent-study baseline in WOMAC Pain at Visit 3E (Week 48)	FAS	Prohibited medications and NSAID/acetaminophen use: treatment policy strategy; analysis will be conducted regardless of use of prohibited medications or NSAID/acetaminophen use.	Difference in the change from parent-study baseline between LOR and placebo using parent-study baseline-adjusted ANCOVA with available data.
	Sensitivity 1	Change from parent-study baseline in WOMAC Pain at Visit 3E (Week 48)	FAS	Prohibited medications and NSAID/acetaminophen use: treatment policy strategy; analysis will be conducted regardless of use of prohibited medications or NSAID/acetaminophen use.	Difference in the change from parent-study baseline between LOR and placebo using parent-study baseline-adjusted ANCOVA with missing data imputed using the MI method.
	Sensitivity 2	Change from parent-study baseline in WOMAC Pain at Visit 3E (Week 48)	mFAS	Prohibited medications and NSAID/acetaminophen use: treatment policy strategy; analysis will be conducted regardless of use of prohibited medications or NSAID/acetaminophen use.	Difference in the change from parent-study baseline between LOR and placebo using parent-study baseline-adjusted ANCOVA with available data.
	Sensitivity 3	Change from parent-study baseline in WOMAC Pain at Visit 3E (Week 48)	PPAS	1) Prohibited medications: principal stratum strategy; subjects who used prohibited medications will be excluded from this analysis. 2) NSAID/acetaminophen: treatment policy strategy; analysis will be conducted regardless of NSAID/acetaminophen use.	Difference in the change from parent-study baseline between LOR and placebo using parent-study baseline-adjusted ANCOVA.
Estimand is repeated using the OA-07-study baseline					

Secondary	Estimator	Variable	Population	Other intercurrent events	Population level summary
	Main	Change from parent-study baseline in WOMAC Function at Visit 3E (Week 48)	FAS	Prohibited medications and NSAID/acetaminophen use: treatment policy strategy; analysis will be conducted regardless of use of prohibited medications or NSAID/acetaminophen use.	Difference in the change from parent-study baseline between LOR and placebo using parent-study baseline-adjusted ANCOVA with available data.
	Sensitivity 1	Change from parent-study baseline in WOMAC Function at Visit 3E (Week 48)	FAS	Prohibited medications and NSAID/acetaminophen use: treatment policy strategy; analysis will be conducted regardless of use of prohibited medications or NSAID/acetaminophen use.	Difference in the change from parent-study baseline between LOR and placebo using parent-study baseline-adjusted ANCOVA with missing data imputed using the MI method.
	Sensitivity 2	Change from parent-study baseline in WOMAC Function at Visit 3E (Week 48)	mFAS	Prohibited medications and NSAID/acetaminophen use: treatment policy strategy; analysis will be conducted regardless of use of prohibited medications or NSAID/acetaminophen use.	Difference in the change from parent-study baseline between LOR and placebo using parent-study baseline-adjusted ANCOVA with available data.
	Sensitivity 3	Change from parent-study baseline in WOMAC Function at Visit 3E (Week 48)	PPAS	1) Prohibited medications: principal stratum strategy; subjects who used prohibited medications will be excluded from this analysis. 2) NSAID/acetaminophen: treatment policy strategy; analysis will be conducted regardless of NSAID/acetaminophen use.	Difference in the change from parent-study baseline between LOR and placebo using parent-study baseline-adjusted ANCOVA.
Estimand is repeated using the OA-07-study baseline					

Secondary	Estimator	Variable	Population	Other intercurrent events	Population level summary
	Main	Change from parent-study baseline in Pain NRS at Visit 2E (Week 24)	FAS	Prohibited medications and NSAID/acetaminophen use: treatment policy strategy; analysis will be conducted regardless of use of prohibited medications or NSAID/acetaminophen use.	Difference in the change from parent-study baseline between LOR and placebo using parent-study baseline-adjusted ANCOVA with available data.
	Sensitivity 1	Change from parent-study baseline in Pain NRS at Visit 2E (Week 24)	FAS	Prohibited medications and NSAID/acetaminophen use: treatment policy strategy; analysis will be conducted regardless of use of prohibited medications or NSAID/acetaminophen use.	Difference in the change from parent-study baseline between LOR and placebo using parent-study baseline-adjusted ANCOVA with missing data imputed using the MI method.
	Sensitivity 2	Change from parent-study baseline in Pain NRS at Visit 2E (Week 24)	mFAS	Prohibited medications and NSAID/acetaminophen use: treatment policy strategy; analysis will be conducted regardless of use of prohibited medications or NSAID/acetaminophen use.	Difference in the change from parent-study baseline between LOR and placebo using parent-study baseline-adjusted ANCOVA with available data.
	Sensitivity 3	Change from parent-study baseline in Pain NRS at Visit 2E (Week 24)	PPAS	1) Prohibited medications: principal stratum strategy; subjects who used prohibited medications will be excluded from this analysis. 2) NSAID/acetaminophen: treatment policy strategy; analysis will be conducted regardless of NSAID/acetaminophen use.	Difference in the change from parent-study baseline between LOR and placebo using parent-study baseline-adjusted ANCOVA.
Estimand is repeated using the OA-07-study baseline					

Secondary	Estimator	Variable	Population	Other intercurrent events	Population level summary
	Main	Change from parent-study baseline in WOMAC Pain at Visit 2E (Week 24)	FAS	Prohibited medications and NSAID/acetaminophen use: treatment policy strategy; analysis will be conducted regardless of use of prohibited medications or NSAID/acetaminophen use.	Difference in the change from parent-study baseline between LOR and placebo using parent-study baseline-adjusted ANCOVA with available data.
	Sensitivity 1	Change from parent-study baseline in WOMAC Pain at Visit 2E (Week 24)	FAS	Prohibited medications and NSAID/acetaminophen use: treatment policy strategy; analysis will be conducted regardless of use of prohibited medications or NSAID/acetaminophen use.	Difference in the change from parent-study baseline between LOR and placebo using parent-study baseline-adjusted ANCOVA with missing data imputed using the MI method.
	Sensitivity 2	Change from parent-study baseline in WOMAC Pain at Visit 2E (Week 24)	mFAS	Prohibited medications and NSAID/acetaminophen use: treatment policy strategy; analysis will be conducted regardless of use of prohibited medications or NSAID/acetaminophen use.	Difference in the change from parent-study baseline between LOR and placebo using parent-study baseline-adjusted ANCOVA with available data.
	Sensitivity 3	Change from parent-study baseline in WOMAC Pain at Visit 2E (Week 24)	PPAS	1) Prohibited medications: principal stratum strategy; subjects who used prohibited medications will be excluded from this analysis. 2) NSAID/acetaminophen: treatment policy strategy; analysis will be conducted regardless of NSAID/acetaminophen use.	Difference in the change from parent-study baseline between LOR and placebo using parent-study baseline-adjusted ANCOVA.
Estimand is repeated using the OA-07-study baseline					

Secondary	Estimator	Variable	Population	Other intercurrent events	Population level summary
	Main	Change from parent-study baseline in WOMAC Function at Visit 2E (Week 24)	FAS	Prohibited medications and NSAID/acetaminophen use: treatment policy strategy; analysis will be conducted regardless of use of prohibited medications or NSAID/acetaminophen use.	Difference in the change from parent-study baseline between LOR and placebo using parent-study baseline-adjusted ANCOVA with available data.
	Sensitivity 1	Change from parent-study baseline in WOMAC Function at Visit 2E (Week 24)	FAS	Prohibited medications and NSAID/acetaminophen use: treatment policy strategy; analysis will be conducted regardless of use of prohibited medications or NSAID/acetaminophen use.	Difference in the change from parent-study baseline between LOR and placebo using parent-study baseline-adjusted ANCOVA with missing data imputed using the MI method.
	Sensitivity 2	Change from parent-study baseline in WOMAC Function at Visit 2E (Week 24)	mFAS	Prohibited medications and NSAID/acetaminophen use: treatment policy strategy; analysis will be conducted regardless of use of prohibited medications or NSAID/acetaminophen use.	Difference in the change from parent-study baseline between LOR and placebo using parent-study baseline-adjusted ANCOVA with available data.
	Sensitivity 3	Change from parent-study baseline in WOMAC Function at Visit 2E (Week 24)	PPAS	1) Prohibited medications: principal stratum strategy; subjects who used prohibited medications will be excluded from this analysis. 2) NSAID/acetaminophen: treatment policy strategy; analysis will be conducted regardless of NSAID/acetaminophen use.	Difference in the change from parent-study baseline between LOR and placebo using parent-study baseline-adjusted ANCOVA.
Estimand is repeated using the OA-07-study baseline					

Other	Estimator	Variable	Population	Intercurrent events	Population level summary
	Main	Change from parent-study baseline in mJSW at Visit 2E (Week 24)	FAS	Prohibited medications and NSAID/acetaminophen use: treatment policy strategy; analysis will be conducted regardless of use of prohibited medications or NSAID/acetaminophen use.	Difference in the change from baseline between LOR and placebo using parent-study baseline-adjusted ANCOVA with available data.
	Sensitivity 1	Change from parent-study baseline in mJSW at Visit 2E (Week 24)	FAS	Prohibited medications and NSAID/acetaminophen use: treatment policy strategy; analysis will be conducted regardless of use of prohibited medications or NSAID/acetaminophen use.	Difference in the change from baseline between LOR and placebo using parent-study baseline-adjusted ANCOVA with missing data imputed using the MI method.
	Sensitivity 2	Change from parent-study baseline in mJSW at Visit 2E (Week 24)	mFAS	Prohibited medications and NSAID/acetaminophen use: treatment policy strategy; analysis will be conducted regardless of use of prohibited medications or NSAID/acetaminophen use.	Difference in the change from baseline between LOR and placebo using parent-study baseline-adjusted ANCOVA with available data.
	Sensitivity 3	Change from parent-study baseline in mJSW at Visit 2E (Week 24)	PPAS	1) Prohibited medications: principal stratum strategy; subjects who used prohibited medications will be excluded from this analysis. 2) NSAID/acetaminophen: treatment policy strategy; analysis will be conducted regardless of NSAID/acetaminophen use.	Difference in the change from parent-study baseline between LOR and placebo using parent-study baseline-adjusted ANCOVA.
Estimand is repeated using the OA-07-study baseline					

Other	Estimator	Variable	Population	Other intercurrent events	Population level summary
	Main	Change from parent-study baseline in WOMAC Total at Visit 3E (Week 48)	FAS	Prohibited medications and NSAID/acetaminophen use: treatment policy strategy; analysis will be conducted regardless of use of prohibited medications or NSAID/acetaminophen use.	Difference in the change from parent-study baseline between LOR and placebo using parent-study baseline-adjusted ANCOVA with available data.
	Sensitivity 1	Change from parent-study baseline in WOMAC Total at Visit 3E (Week 48)	FAS	Prohibited medications and NSAID/acetaminophen use: treatment policy strategy; analysis will be conducted regardless of use of prohibited medications or NSAID/acetaminophen use.	Difference in the change from parent-study baseline between LOR and placebo using parent-study baseline-adjusted ANCOVA with missing data imputed using the MI method.
	Sensitivity 2	Change from parent-study baseline in WOMAC Total at Visit 3E (Week 48)	mFAS	Prohibited medications and NSAID/acetaminophen use: treatment policy strategy; analysis will be conducted regardless of use of prohibited medications or NSAID/acetaminophen use.	Difference in the change from parent-study baseline between LOR and placebo using parent-study baseline-adjusted ANCOVA with available data.
	Sensitivity 3	Change from parent-study baseline in WOMAC Total at Visit 3E (Week 48)	PPAS	1) Prohibited medications: principal stratum strategy; subjects who used prohibited medications will be excluded from this analysis. 2) NSAID/acetaminophen: treatment policy strategy; analysis will be conducted regardless of NSAID/acetaminophen use.	Difference in the change from parent-study baseline between LOR and placebo using parent-study baseline-adjusted ANCOVA.
Estimand is repeated using the OA-07-study baseline					

Other	Estimator	Variable	Population	Other intercurrent events	Population level summary
	Main	Change from parent-study baseline in WOMAC Stiffness at Visit 3E (Week 48)	FAS	Prohibited medications and NSAID/acetaminophen use: treatment policy strategy; analysis will be conducted regardless of use of prohibited medications or NSAID/acetaminophen use.	Difference in the change from parent-study baseline between LOR and placebo using parent-study baseline-adjusted ANCOVA with available data.
	Sensitivity 1	Change from parent-study baseline in WOMAC Stiffness at Visit 3E (Week 48)	FAS	Prohibited medications and NSAID/acetaminophen use: treatment policy strategy; analysis will be conducted regardless of use of prohibited medications or NSAID/acetaminophen use.	Difference in the change from parent-study baseline between LOR and placebo using parent-study baseline-adjusted ANCOVA with missing data imputed using the MI method.
	Sensitivity 2	Change from parent-study baseline in WOMAC Stiffness at Visit 3E (Week 48)	mFAS	Prohibited medications and NSAID/acetaminophen use: treatment policy strategy; analysis will be conducted regardless of use of prohibited medications or NSAID/acetaminophen use.	Difference in the change from parent-study baseline between LOR and placebo using parent-study baseline-adjusted ANCOVA with available data.
	Sensitivity 3	Change from parent-study baseline in WOMAC Stiffness at Visit 3E (Week 48)	PPAS	1) Prohibited medications: principal stratum strategy; subjects who used prohibited medications will be excluded from this analysis. 2) NSAID/acetaminophen: treatment policy strategy; analysis will be conducted regardless of NSAID/acetaminophen use.	Difference in the change from parent-study baseline between LOR and placebo using parent-study baseline-adjusted ANCOVA.
Estimand is repeated using the OA-07-study baseline					

Other	Estimator	Variable	Population	Other intercurrent events	Population level summary
	Main	Change from parent-study baseline in WOMAC Total at Visit 2E (Week 24)	FAS	Prohibited medications and NSAID/acetaminophen use: treatment policy strategy; analysis will be conducted regardless of use of prohibited medications or NSAID/acetaminophen use.	Difference in the change from parent-study baseline between LOR and placebo using parent-study baseline-adjusted ANCOVA with available data.
	Sensitivity 1	Change from parent-study baseline in WOMAC Total at Visit 2E (Week 24)	FAS	Prohibited medications and NSAID/acetaminophen use: treatment policy strategy; analysis will be conducted regardless of use of prohibited medications or NSAID/acetaminophen use.	Difference in the change from parent-study baseline between LOR and placebo using parent-study baseline-adjusted ANCOVA with missing data imputed using the MI method.
	Sensitivity 2	Change from parent-study baseline in WOMAC Total at Visit 2E (Week 24)	mFAS	Prohibited medications and NSAID/acetaminophen use: treatment policy strategy; analysis will be conducted regardless of use of prohibited medications or NSAID/acetaminophen use.	Difference in the change from parent-study baseline between LOR and placebo using parent-study baseline-adjusted ANCOVA with available data.
	Sensitivity 3	Change from parent-study baseline in WOMAC Total at Visit 2E (Week 24)	PPAS	1) Prohibited medications: principal stratum strategy; subjects who used prohibited medications will be excluded from this analysis. 2) NSAID/acetaminophen: treatment policy strategy; analysis will be conducted regardless of NSAID/acetaminophen use.	Difference in the change from parent-study baseline between LOR and placebo using parent-study baseline-adjusted ANCOVA.
Estimand is repeated using the OA-07-study baseline					

Other	Estimator	Variable	Population	Other intercurrent events	Population level summary
	Main	Change from parent-study baseline in WOMAC Stiffness at Visit 2E (Week 24)	FAS	Prohibited medications and NSAID/acetaminophen use: treatment policy strategy; analysis will be conducted regardless of use of prohibited medications or NSAID/acetaminophen use.	Difference in the change from parent-study baseline between LOR and placebo using parent-study baseline-adjusted ANCOVA with available data.
